- 12) Inability to comply with study procedures
- 13) Prior coronary artery calcium score and/or coronary CT angiogram

DURATION OF STUDY ENROLLMENT: 12 months

SAMPLE SIZE (total enrollment): 175 subjects

3. OBJECTIVES AND SPECIFIC AIMS:

Prior to undergoing CCTA, non-contrast CT scanning of the entire heart is usually performed in adults over 50-years of age in order to assess for the presence and severity of coronary artery calcium. By providing a modified CT scan with a reduced length the same data can be obtained by the imager to ensure a high quality scan while decreasing the patient's overall radiation exposure. Our objectives and specific aims to validate our hypothesis include:

- To assess the impact on CCTA image quality using modified calcium score approach
- To determine the rate of changes in the coronary CT angiography acquisition parameters after evaluation of the modified versus standard calcium scoring scout series. Significant changes in CCTA acquisition include any of the following as compared to recommended CCTA parameters prior to scout CT performance: a change (increase or decrease) in tube current (mA) by 50, any change in tube potential (kV), change to/from retrospectively-gated CCTA, any change in padding (acquisition window), or changing to/from a high definition CT scan acquisition.
- To assess the difference in patient estimated effective radiation exposure (mSv) between the modified versus standard calcium scoring techniques.
- To assess the difference in patient estimated effective radiation exposure (mSv) of the entire CCTA study (plus calcium scoring) between groups.
- .

4. BACKGROUND AND SIGNIFICANCE:

4.1 Literature Review.

Cardiovascular disease is the leading cause of mortality and morbidity in the United States. The impact of coronary disease on our society has prompted increased emphasis on primary prevention. To identify the patients who would benefit the most from primary prevention, such as

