Based on the above information, non-contrast CT scanning of the entire heart is usually performed in adults over 50-years of age in order to assess for the presence and severity of coronary artery calcium. This is performed so to identify patients with high degrees of coronary calcium such that the imagers may modify the scan parameters of the subsequent coronary CTA scan in order to optimize image quality and diagnostic accuracy of CCTA. Specific variables that may be adjusted on the subsequent CCTA scan based on the absence or presence and severity of CAC include: tube current (mA), tube potential (kV), use of high-definition scanning, and type of ECG gating/triggering. Of note, the performance of non-contrast CT scan prior to CCTA is typically done using the well-established Agatston method. In this method, the entire heart is scanned using a relatively high tube potential of 120 kV. While this higher tube potential may not be needed to identify calcium, it is a prerequisite in order to calculate an Agatston coronary artery calcium score and is therefore the standard method to perform non-contrast scanning prior to CCTA in our lab and most labs worldwide. Given that the prognostic value of CCTA is superior to calcium scoring, many wonder if the type of non-contrast scan should be modified in order to reduce patient radiation

exposure.

Importantly, it has been demonstrated that the majority of coronary artery calcification occurs in the proximal to mid portions of the coronary arteries¹³. This important fact suggests that a more focused field of view during scout non-contrast CT imaging prior to CCTA may be effective as scanning the entire heart while limiting radiation exposure.

Radiation Exposure

The Society of Cardiovascular Computed Tomography (SCCT) guidelines on radiation dose and dose-optimization strategies in cardiovascular CT states that the imager should attempt to limit the radiation dose to the lowest reasonable level while acquiring as much information as possible in the diagnosis and characterization of a patient's coronary artery disease.

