5.7.2 Sample Size Estimation

The proposed sample size is 158 based on sample size calculations for aim 1, as described below.

Power and sample size for aim 1 is based on a standard deviation of radiation exposure of 3 to 3.5 mSv, based on clinical experience, and an anticipated 40% reduction in exposure from 4 to 2.4 mSv. A sample size of 154 (77 per group) will have 80% power to detect a difference in radiation exposure of 1.6 mSv if the standard deviation is 3.5, based on a t test for independent samples with a 5%, two-sided significance level.

Examining power analyses for a noninferiority studies, assuming that the full and reduced methods will produce similar outcomes for image quality and any change in CCTA parameters:

--For the comparison of image quality (aim 1), it is assumed that the image quality for the full method will be 3.2 (standard deviation = 1.1). This study will have power of 80% to show that the mean for the reduced method is at least as high as the mean for the full method. This assumes that the mean image quality scores for the full and reduced populations are 3.20 and 3.15 respectively, with a common within-group standard deviation of 1.10, that a difference of 0.49 points or less is unimportant, that the sample size in the two groups will be 79 and 79, and that

alpha (1 tailed) is set at .05. To accrue complete data 158 subjects, a total of sample size of up to 175 will be recruited to account for a 10% dropout rate for technical difficulties.

--This study will have 81% power to show that the event rate (event rate = any change in CCTA parameters) for the reduced method is at least as low as the event rate for the full method. This assumes that the event rates for the full and reduced method populations are precisely equal (at 50.0%), that a difference of 20% points or less is unimportant, that the sample size in the two groups will be 79 and 79, and that alpha (1 tailed) is set at .05.

While a 20% difference is relatively large, to detect a smaller difference between groups (i.e. difference of 10-15%) using the same assumptions, would require hundreds of subjects.

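### The Aim 2 power statement bounds only an excess of CCTA parameter changes with the modified scan; a shortfall, which the protocol's rationale makes at least as important to exclude, is left unbounded

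*Combined protocol and SAP*

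**What the plan says.** Section 5.7.2 introduces two non-inferiority power calculations by saying that the two scan methods are expected to perform alike. For Aim 2 the outcome is defined as "event rate = any change in CCTA parameters". The claim is "This study will have 81% power to show that the event rate" "for the reduced method is at least as low as the event rate for the full method". The assumptions are a 50% rate in both groups, "that a difference of 20% points or less is unimportant", "that the sample size in the two groups will be 79 and 79", and a one-tailed alpha of 0.05. The matching statement for image quality runs the other way (the reduced method at least as high), so a favourable direction is stated for each outcome.

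The rationale is given elsewhere:

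- Section 2.1 sets the purpose as comparing the two scans for detecting calcification that may affect the CCTA.
- Section 3 expects no loss of information: "By providing a modified CT scan with a reduced length the same data can be obtained by the imager".
- Section 4.1, on the role of calcium scoring, says the scan is done to identify heavy calcification so that "the imagers may modify the scan parameters of the subsequent coronary CTA scan in order to optimize image quality and diagnostic accuracy of CCTA".
- Section 4.1, on radiation exposure, warns that without the calcium scan the imager loses information bearing on acquisition settings and on whether to abort.

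Section 5.7 sends the analysis to table 5.7.1. Its Aim 2 row lists five yes/no components and Fisher's exact test, with no margin and no non-inferiority rule. Section 5.8 makes parameter changes a secondary endpoint.

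**The concern.** In the power statement a parameter change is handled like an adverse outcome: the fewer, the better. In the rationale it is the useful product of the scan. The modified scan covers less of the heart and uses a lower tube voltage (Section 5.5), so one plausible way for it to fall short is to show less calcium and prompt fewer calcium-driven adjustments. A hypothesis with an upper bound only cannot exclude that; it reads a lower rate as a better result. It also cannot support a claim that the two methods perform alike, because such a claim has two sides.

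At stake is the interpretation of the comparative endpoint closest to the purpose in Section 2.1. Bringing table 5.7.1 into line with 5.7.2 as worded would carry the one-sided direction into the analysis.

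**Working it through.** **Inputs, all from Section 5.7.2:** n = 79 per arm, standard rate 0.50, margin 0.20, one-sided alpha 0.05 (z = 1.645). Modified rates below 50% are assumed scenarios; the documents give none.

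**Step 1: reproduce the stated power.** With the unpooled normal approximation, SE = sqrt(0.5×0.5/79 + 0.5×0.5/79) = 0.0796. Power = Φ(0.20/0.0796 − 1.645) = Φ(0.87) = 80.8%. Exact binomial enumeration of the same rule gives 80.9%. The stated 81% is confirmed, and so is the one-sided reading.

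**Step 2: the stated criterion when the modified rate is lower.** Let d = modified − standard.

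- Stated criterion (upper limit below +20 points): probability = Φ((0.20 − d)/SE − 1.645).
- Lower-side criterion (lower limit above −20 points): probability = Φ((0.20 + d)/SE − 1.645).

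For a modified rate of 30%, d = −0.20 and SE = sqrt((0.25 + 0.21)/79) = 0.0763.

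- Stated criterion: Φ(0.40/0.0763 − 1.645) = Φ(3.60) = 99.98%.
- Lower-side criterion: Φ(0 − 1.645) = 5%. This equals alpha by construction, because the true difference sits on the margin.

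| Assumed modified rate (standard 50%) | Meets 5.7.2 criterion | Meets lower-side criterion | Meets both sides (exact) | Fisher p < 0.05, two-sided (exact) |
|---|---|---|---|---|
| 50% | 80.8% | 80.8% | 62% | 3% |
| 40% | 98.5% | 35% | 33% | 19% |
| 30% | 99.98% | 5% | 4.6% | 68% |
| 20% | about 100% | 0.1% | 0.1% | 97% |
| 10% | about 100% | about 0% | about 0% | about 100% |

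The Fisher column assumes a two-sided 0.05 level and application to the any-change composite; table 5.7.1 states neither.

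**Step 3: power of the alternatives at equal 50% rates.**

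- Lower side only: 80.8%, unchanged by symmetry.
- Both sides (two one-sided tests): 2 × 0.8076 − 1 = 61.5% (exact 61.8%).
- Sample size for 80% power on both sides: 2 × 0.25 × (1.645 + 1.282)²/0.20² = 107.1, so 108 per arm and 216 in total. With the plan's 10% dropout, 216/0.9 = 240.

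**The case against.** A reader might infer that a modified scan that missed calcium and prompted no changes would be declared non-inferior, so that Aim 2 cannot be answered. The documents do not support going that far, for three reasons.

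- **No analysis rule issues that verdict.** Sections 5.7 and 5.7.3 send Aim 2 to table 5.7.1, which has Fisher's exact test and no success criterion. Under the assumptions above, that test would almost certainly flag a fall from 50% to 10% or less, and would flag a fall to 30% about two times in three.
- **Missed calcium need not lower the rate.** Section 3 and table 5.7.1 count mA increases and decreases, and moves to or from retrospective gating and high definition. Section 4.1 says the absence of calcium can also prompt an adjustment. The documents do not fix the net direction.
- **The endpoint is secondary, and harm could show elsewhere.** Section 5.7.2 ties the sample size to Aim 1. Blinded image quality is primary, cancellation is a separate secondary endpoint, and visible calcification and CCTA plaque are recorded by segment.

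These points stand, and they limit the consequence and the severity. They do not justify the direction. The only success statement for the any-change rate is in 5.7.2, and it would read a significant drop as favourable. That changes count both ways is a reason to look at both sides, not to bound the upper one alone. Image quality, with its 0.49-point margin, does not measure calcium detection.

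**Conclusion.** The direction of the Aim 2 hypothesis conflicts with the protocol's own rationale and should be corrected. If 5.7.2 is used to interpret Aim 2, a fall in the change rate from 50% to 30% meets the criterion with probability above 99.9%, against 5% for a lower-side criterion. Fisher's test may reveal the drop (about 68% if two-sided), but the stated hypothesis would still class it as success.

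The size rests on the plan's 50% rate, 20-point margin and 79 per arm, and on assumed lower rates for the modified scan. The stated 81% power is arithmetically correct. This is a point that should be fixed, not a fatal one: the endpoint is secondary, and the planned test does not itself produce a non-inferiority verdict. It does not establish that a poor scan must yield fewer changes, or that Aim 2 is unanswerable.

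**What to change.** In 5.7.2, and in the Aim 2 row of table 5.7.1, name the any-change composite, report the 90% confidence interval for modified minus standard, and state the interval method. Require at least that the lower limit lies above −20 points, and report the upper limit as well. Sample size, margin and 81% power are unchanged, so the cost is wording only.

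Because changes are counted in both directions and the plan expects the methods to perform alike, the sponsor may instead require the whole interval to lie within ±20 points. The stated power must then be about 62% with 79 per arm; 80% would need 108 per arm, or 240 recruited with 10% dropout.

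Under either version a fall of just under 20 points still counts as unimportant, and the rate does not show whether the changes were appropriate. The plan should say that Aim 2 will not be described as showing equal calcium detection.

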5.7.3 Data Analysis Plan

1. A patient flow diagram as per CONSORT guidelines will be provided to present the number of subjects recruited, screened, refusals or subjects excluded (with reasons), randomized, lost to follow up, etc. Beginning and ending months of recruitment will be described.
2. A table of baseline demographic and clinical characteristics will be presented for the full and reduced scan groups to include means with standard deviations for continuous normally distributed variables, medians with interquartile ranges for ordinal data and counts with percentages for categorical data. Groups may be compared using two sample t-tests, Wilcoxon rank sum tests or Fisher's exact test as appropriate.
3. Interrater reliability for quality scores will be examined using the Kappa statistic.
4. Univariate comparison of the primary and secondary endpoints are described above in the Data Analysis table.
5. Multivariate analysis of the quality score will include ordinal regression, with the concensus quality score (on a scale from 1 to 4) as the dependent variable and the independent variables to include demographic and clinical factors known to affect CCTA quality, such as BMI, breath-holding, resting heart rate, use of nitroglycerin, etc.

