5.5 Study Methodology/Procedures

5.5 Methods:

The FOCUS-CCTA study will be a prospective, randomized single center single cohort study to evaluate the diagnostic and clinical implications of modified scan length calcium scoring versus the standard scan length calcium scoring in CCTAs using a MDCT scanner. Significant diagnostic and clinical implications include the quality of the study in the modified versus standard scan length; changes in the cardiac CT after evaluation of the modified or standard calcium scoring (These changes include: a change in mA by 50, any change in kV, any changes

in padding and changing to high definition.); cancellation of the study and a comparison of the radiation received by each patient.

CCTA Study Design:

Patients who are scheduled for CT coronary angiography for evaluation of clinically suspected coronary artery disease who are fifty years old or older without known coronary artery disease and without a previous calcium score will be prospectively included in this study. The indications for CT coronary angiography will be used in accordance with the ACCF/SCCT/ACR/AHA/ASE/ASNC/NASCI/SCAI/SCMR Appropriate Use Criteria for Cardiac Computed Tomography. Exclusion criteria will include patients who are not able to obtain angiography to include: previous anaphylactoid reaction to iodinated contrast material and renal insufficiency (verified by a renal panel within 30 days of the procedure).

In accordance with standard operating procedures for CCTA (joint Cardiology-Radiology program), patients will arrive to the cardiovascular preparation area (“Prep and Recovery”, Building 9A) and will receive a clinical assessment with vital signs by a physician and nursing staff. Patients without a contraindication to B-adrenergic blocking agents and/or calcium channel blocking agents (will be given a beta-blocker either by oral intake or intravenously prior to the exam to obtain a goal heart rate between 50-65 bpm). Once the patients are within this window they will be escorted to radiology, in accordance with standard CCTA policies. During the preparation time eligible patients will be consented by [name] and will be randomized at that time. The patient’s chart will have an envelope with it that describes which investigational arm the patient will be in. The radiologist and cardiologist will view the card in the envelope after making their initial decision on the parameters for the CCTA.

CT Protocol

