All CT examinations will be performed on standard multi-detector CT machines typically utilized for CCTA, in accordance with SCCT guidelines. Prior to any imaging, both the radiologist and cardiologist (non-study personnel) clinically performing the CCTA will fill out a form choosing their initial proposed CCTA acquisition parameters (type of gating, mA, kV, padding, use of high-definition scanning) based on the patient’s age, sex, BMI and achieved pre-scan heart rate, as is typical of all CCTA examinations. Then antero-posterior and lateral topograms of the chest will be obtained to plan subsequent data acquisition, as required for all CCTA examinations. Based on randomization, either a modified or standard calcium scoring series will be performed: Subjects will be randomized in a 1:1 ratio to either modified or standard calcium scoring using a computer program based on random number generation. Assignments will be concealed in sequentially numbered opaque sealed envelopes (SNOSE). The randomization assignment and envelopes will be prepared by a person who is not involved

in the recruitment process or clinical conduct or interpretation of the non-contrast studies or CCTA.

In patients randomized to standard coronary artery calcium scoring, this scan will be performed in usual axial fashion obtained at 70% of the R-R interval using the following parameters: rotation time 0.35 sec; collimation of 64 x 0.625mm; detector coverage of 20.0 mm; axial thickness 2.5; tube voltage, 120 kV and tube current 250mA. The scan length, in accordance with current protocol, will be from 1 cm below the carina through the diaphragms.

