5.7 Statistical Considerations

The statistical evaluation will be performed as seen in the Data Analysis table below in 5.7.1. Of note, all outcomes compare the full and reduced scan groups.

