5.7.1 Data Analysis Table

Aim 1- To assess the impact on CCTA image quality using modified calcium score approach.	
 - Image quality (4 point scale) - Signal/noise ratio 	
 - Treatment group - Treatment group 	
 - Two sample t-test or Mann-Whitney (dependent upon the distribution of the data). - Two sample t-test
Aim 2- To determine the rate of changes in the coronary CT angiography acquisition parameters of the modified versus standard calcium scoring	
 - Change in (increase or decrease) in tube current (mA) by 50 - Any change in tube potential (kV) - Change to/from retrospectively-gated CCTA - Any change in padding (acquisition window) - Changing to/from a high definition CT acquisition 	
 - Treatment group 	
 - Fisher's exact test

	All answered as yes/no		
Aim 3- To assess the difference in patient estimated effective radiation exposure (mSv) between the modified versus standard calcium scoring techniques.	- Average of radiation exposure (mSv)	- Treatment group	- Two sample t-test
Aim 4- To assess the difference in patient estimated effective radiation exposure (mSv) of the entire CCTA study (plus calcium scoring) between groups.	- Average of radiation exposure (mSv)	- Treatment group	- Two sample t-test

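### The primary image-quality comparison is sound but unadjusted; pre-specifying age, sex, BMI and pre-imaging heart rate as covariates would buy modest precision at almost no cost

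*Combined protocol and SAP*

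**What the plan says.** **Primary comparison.** For Aim 1, the Data Analysis Table (5.7.1) lists the four-point quality score with treatment group as the only factor and, as the test, "Two sample t-test or Mann-Whitney (dependent upon the distribution of the data". Item 4 of 5.7.3 confirms that the comparison is unadjusted: "Univariate comparison of the primary and secondary endpoints are described above in the Data Analysis table".

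**Multivariable model.** Item 5 of 5.7.3 adds an ordinal regression with the "concensus quality score (on a scale from 1 to 4) as the dependent variable" and "independent variables to include demographic and clinical factors known to affect CCTA quality, such as BMI, breath-holding, resting heart rate, use of nitroglycerin", followed by an open-ended etc. Treatment arm is not in that list.

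**What is known before the arm is revealed.** Under CT Protocol in 5.5, the clinical radiologist and cardiologist propose acquisition parameters before any imaging, on the basis of "age, sex, BMI and achieved pre-scan heart rate". Under CCTA Study Design, "The radiologist and cardiologist will view the card in the envelope after making their initial decision on the parameters for the CCTA". The data sheets in 5.5.5 collect age, gender, height and weight, and heart rate before and after the scan.

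**Outcome.** Section 5.5 scores quality by segment (18-segment model, 1 to 4) and defines the patient's overall quality as the mean of the consensus segment scores.

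**The concern.** In a trial of 79 analysed patients per arm, covariates that predict the outcome and are fixed before the arm is known can narrow the confidence interval for the arm effect without more patients. The plan holds four such variables. It says that BMI and heart rate affect quality, and that all four drive the choice of acquisition parameters. Yet it uses none of them in the comparison that answers its primary question. At stake is the width of the interval around the quality difference, and hence the chance of ruling out the 0.49-point loss that 5.7.2 treats as the limit of unimportance.

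Separately, item 5 cannot be run by a second analyst as it stands, because arm, the final covariate list and the outcome level are left open. This is a smaller wording matter.

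**Working it through.** **Inputs from 5.7.2:** means 3.20 and 3.15 (true difference 0.05), SD 1.10, margin 0.49, 79 per arm, one-sided alpha 0.05. **Assumed, because the documents are silent:** R² of the four covariates (0 to 0.2) and the within-patient correlation (ICC) of segment scores.

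**1. The plan's own figure.** SE = 1.10 × √(2/79) = 0.175. Noncentrality = (0.49 − 0.05)/0.175 = 2.514. Noncentral-t power on 156 df is 80.5%, against the stated 80%. It reproduces, and it rests on the full SD with no covariates. The 90% CI half-width is 1.655 × 0.175 = 0.290.

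**2. With four covariates fitted.** Two things change.
- The residual SD becomes 1.10 × √(1 − R²).
- Chance imbalance in the covariates inflates the variance by about (158 − 3)/(158 − 3 − 4) = 155/151 = 1.0265, so the SE rises by a factor of 1.013. Error df fall to 158 − 6 = 152.

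Adjusted noncentrality = 2.514/√(1.0265 × (1 − R²)).

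| Assumed R² | Noncentrality | Adjusted power | Change from 80.5% | 90% CI half-width |
|---|---|---|---|---|
| 0 | 2.48 | about 79.5% | −1 point | 0.293 |
| 0.05 | 2.55 | about 81% | under +1 point | 0.286 |
| 0.10 | 2.62 | about 83% | about +3 points | 0.278 |
| 0.20 | 2.77 | about 87% | about +6 points | 0.262 |

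Simulation of the fitted regression (40,000 trials per cell) agrees: 79.4%, 81.0%, 83.5% and 86.9%. Adjustment breaks even where 1 − R² = 151/155, that is R² = 0.026, or near 0.03.

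**3. Is 1.10 plausible as the SD of a patient mean?** On a 1-to-4 scale with mean 3.2, no score can have an SD above √(0.8 × 2.2) = 1.327. With 18 equally correlated segments, patient-mean variance = segment variance × (1 + 17 × ICC)/18. A patient-mean SD of 1.10 therefore needs ICC ≥ (18 × 1.21/1.76 − 1)/17 = 0.67. If 1.10 is instead the segment SD, the patient-mean SD is 0.54 at ICC 0.2 and 0.80 at ICC 0.5. At SD 0.80 the unadjusted power is already 96.4%. Adjustment at R² = 0.2 takes it to about 98% and narrows the half-width from 0.211 to 0.191.

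**4. Item 5.** Set against the rest of the protocol:
- *Arm* is not listed, but 5.7 says that "all outcomes compare the full and reduced scan groups", so it may be intended.
- *Nitroglycerin* is given to all patients under 5.5, so it has no planned variation and drops out.
- *Breath-holding* is on neither data sheet, and the time of its assessment is not stated.
- *Outcome level* is open. A mean of 18 integer scores has 72 − 18 + 1 = 55 possible values, which is not a four-level outcome. The segment scores are four-level but cluster within patient. The clinical team also gives a four-level overall score per patient, though that score is not described as a consensus.

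**The case against.** An unadjusted two-group test is a legitimate primary analysis under concealed 1:1 randomisation. That stands. A reader might infer from the lack of covariates that the comparison is biased or underpowered; the documents support neither.

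The gain depends on an R² that the plan does not give, and there are reasons to expect a small one. Heart rate is actively managed "to obtain a goal heart rate between 50-65 bpm", and acquisition parameters are already tailored to the same four factors. If the patient-mean SD is well below 1.10, adjustment will hardly affect the non-inferiority conclusion. All of this stands and limits the claim to a modest one.

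Two details also stand. The pre-imaging form in 5.5 records the proposed acquisition parameters; it is not said to record the four factors, which come from the data sheets in 5.5.5. Those sheets do not say which scan the earlier heart-rate value precedes, so its timing must be defined before it is used.

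It is also tempting to read item 5 as leaving arm out on purpose, or as treating segments as independent. The plan says neither. The item is supplementary and its list is illustrative, so its gaps call for clarification and do not carry this point.

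What the objection does not remove is that the covariates are already collected, and that the likely loss from using them is about one point of power.

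**Conclusion.** This is a low-cost improvement and not an error. The primary comparison is unbiased, and the 80% power figure is arithmetically right for the calculation in 5.7.2. Pre-specified adjustment would change power by about −1 to +6 points for assumed R² of 0 to 0.2, if the patient-mean SD is 1.10. If that SD is nearer 0.8, the benefit is mainly an interval about 10% narrower at R² = 0.2 (0.191 against 0.211). Confidence in the size is moderate, because R² and the within-patient correlation are assumptions.

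The reproduced 80% should not be read as the power of the test listed in 5.7.1. It belongs to a comparison against a margin of 0.49, which that table does not name. That gap is a separate issue, and covariate adjustment does not by itself resolve it.

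**What to change.** Pre-specify, before data are examined:

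1. **Primary model.** Linear regression of the patient-mean quality score on arm, age, sex, BMI (from height and weight) and the heart rate achieved before any imaging. State that this is the earlier of the two heart-rate values on the data sheet.
2. **Inference.** Report the adjusted difference (modified minus standard) with its 90% CI and compare the lower limit with -0.49, the margin in 5.7.2.
3. **Support.** Keep the unadjusted comparison (t-test, or Mann-Whitney if the distribution requires it) as a supporting result.
4. **Quantitative measures.** Use the same covariates for signal, noise and contrast-to-noise ratio.
5. **Item 5 wording (minor).** Name arm, omit nitroglycerin and breath-holding from the model, and state whether the outcome is the patient mean or the segment score. If it is the segment score, allow for clustering within patient.

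The cost is analysis-plan wording and a little programming, with no new data items. If the covariates explain nothing, power falls from 80.5% to about 79.5%.
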